**13) Provisions to Monitor the Data to Ensure the Safety of Subjects\***

We do not expect for this study to create more than minimal risk for the participating families. Yet, the study will be monitored by the study investigators and/or sponsors. In addition, a formally constituted Scientific Advisory Board will help monitor the study if additional advice is needed.

#### 14) **Withdrawal of Subjects\***

Participants will be told that this study is completely voluntary and that they have the right not to participate in any intervention procedure. They also can completely withdraw from the study at any time without any negative consequences.

In past studies, we have not had to withdraw subjects. There is potential for withdrawal of subjects if the adolescent is arrested, reports suicidal ideation, or some other extreme adverse event. If a subject is arrested, reports suicidal ideation, or some other extreme adverse event, a qualified study personnel, i.e., the clinical supervisor, may ask them to please withdraw from the study, and if appropriate, refer them to the correct treatment.

According to IRB, if a subject becomes incarcerated while enrolled in a study, all research interactions and interventions with that subject, and the obtaining of identifiable private information about the subject must cease.

#### 15) **Risks to Subjects\***

We do not expect that there will be any negative consequences from participating in this study. However, the sensitive nature of some intervention topics (e.g. sexual behaviors and drug use) may be embarrassing and/or distressing to some participants. It is also possible that they may feel tired or fatigued after answering the questionnaires, or made uncomfortable by the questions that are asked. In addition, STI testing may involve minimal physical discomfort for the adolescent. Being tested for STIs may also cause anxiety for the adolescent and/or parent regardless of the adolescent's test results. Receiving positive results may make the adolescent and/or parent very upset. If the test is negative, there is still the possibility that the adolescent could be infected with an STI and test positive at some time in the future. Also, it is always possible that the test results could be invalid. Should an adolescent test positive for gonorrhea and/or chlamydia, the facilitator, with guidance from the clinical supervisor, a licensed clinical social worker, and principal investigator, will work with the adolescent on how to process disclosure of the positive test result to the parent or legal guardian. If after discussions with the facilitator and clinical supervisor, the adolescent still refuses to disclose (the law in FL does not require parents to be notified of STI infection) because s/he fears negative consequences such as being thrown out of the house or severe family discord, the facilitator and clinical supervisor will work with the adolescent to connect her/him to proper treatment. If an adolescent tests positive for an STI, we are required, by Florida law, to report the result to the Florida Department of Health.

If a parent or adolescent reports elevated levels of depression, or if an adolescent reports incidence of bullying, he or she will be directed to speak with a facilitator for further assessment. If necessary, a referral will be made for additional services.

**16) Potential Benefits to Subjects\***

There may be direct benefits to participating in this study. Depending on which intervention participants are assigned to, adolescents may be less likely to use drugs and engage in risky behaviors such as having sex without a condom. Additionally, depending on the intervention, families may communicate more effectively.

**17) Vulnerable Populations\***

The research involves children under the age of 18. To avoid coercion or undue influence, the adolescents will assent and complete assessments separate from their primary care giver. In case the adolescent does not want to assent, the family will be told they did not meet one or more of the inclusion/exclusion criteria but the facilitator will not reveal to the parent that the child did not assent (to avoid any consequences to the child).

**19) Community-Based Participatory Research\***

Not applicable.

**20) Sharing of Results with Subjects\***

Youth will be encouraged to refer sex partners for treatment. The county health department will be notified of reportable STIs. The subjects, county health department will be notified via phone call or in-person by a study personnel team member.

**21) Setting**

The research team will identify and recruit potential subjects in nine pediatric clinics. The first site is an academic pediatric clinic within the University of Miami's Health District. This practice serves mostly insured individuals. The second pediatric clinic we have partnered with is a mobile clinic that provides medical care at no charge to uninsured youth. Both of these clinics participated in our pilot feasibility and acceptability study. The third and fourth sites are private pediatric care clinic. These sites serve mostly insured youth. The fifth clinic is Jackson Memorial Medical Center, a general community clinic in Miami. The sixth clinic is UHealth Kendall which is a part of the UM system. The seventh clinic is Nicklaus Children's Hospital, a private

hospital located in Miami-Dade. The eighth and ninth clinics are pediatric centers serving the S. Florida community, Borinquen Medical Centers and Prime Care Family Centers. All recruitment, consent/assent, baseline assessment, and randomization will occur in one of the clinics. The intervention will be delivered via the Internet, thus subjects will most likely be in their homes or a place with Internet capabilities (e.g. school, library) to receive the intervention. The follow up assessments and STI testing will take place on the University of Miami Miller School of Medicine Campus, one of the clinic sites, or the participant's homes.

Assessors will be assigned to each of the pediatric care clinics. Each of the pediatric care clinics will have one pediatric care facilitator (nurse assistant, licensed clinical social worker, mental health counselor). Assessor and/or facilitators will be responsible for screening potential study participants. Assessors are responsible for conducting the parent and youth assessments over the five years. The assessor will also be responsible for scheduling these assessments. Finally, the assessor will also be responsible for maintaining cordial contact in between assessment time points, in order to maximize retention rates at assessments. They will also be responsible for tracking family completion of online sessions and progression through the intervention.

Other study personnel, such as student and research assistants will be trained in study operating procedures, including consent/assent. All study personnel members are CITI trained and are adequately informed about the protocol, research procedures, and their duties and functions. Trainings will be held for study personnel members before the beginning of the study in: protocol, research procedures, and assessments. Study personnel will be asked to role play procedures at the training. If more training is needed, they will be trained again throughout the study. All of the study personnel have been involved in NIH funded studies and are all familiar with the recruitment/study procedures as those being proposed. Regardless of experience, trainings will still be held by the lead clinical supervisor and principal investigator to assure all study personnel members are adherent to the study procedures. Weekly meetings will also be held to discuss study updates, issues or concerns.

(b) Resources Available

The physicians and trained mental health professionals from the clinics are the medical and/or psychological resources for the subjects. We only anticipate that the subjects are in need of these resources, outside of their usual use, if they test positive for an STI. The clinic sites are: UHealth Pediatrics at the Professional Arts Center, University of Miami Pediatric Mobile Clinic, UHealth at Kendal, Ambulatory Care Center West Pediatrics at Jackson Memorial Hospital, Kidstown Pediatrics, LLC, Nicklaus Children's Hospital, South Florida Pediatric Partners, Borinquen Medical Centers, and Primecare Family Centers.

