The four virtual family sessions will be conducted by a trained study team member or pediatric staff member (elsewhere, "Facilitator") according to the same protocol used in the face-to-face Familias Unidas intervention. However, eHealth Familias Unidas will use online video conferencing technologies to virtually recreate the therapeutic environment of the family session. The sessions are delivered via the Internet utilizing webcams and a videoconferencing software called VSee. eHealth Familias Unidas Primary Care facilitators will be responsible for scheduling and delivering the four online family sessions with each of their families. The online family sessions will provide parents the opportunity to practice with their adolescent the skills that they learned in the mock parent group sessions. The content of each of these four family sessions is identical to that of face-to-face Familias Unidas. Virtual family sessions will be conducted in Spanish and/or English so to accommodate the language preferences of the parent and adolescent participants of each family session. Pending parent and adolescent consent and assent, all virtual family sessions will be video-recorded via VSee. All recorded sessions will be stored in secure University of Miami servers and will be labeled with the family's case ID. The recordings will only be used for purposes of clinical supervision, research and training—provided participant consent/assent.

A log-in procedure accessed through the Familias Unidas website will serve as the mechanism by which to ensure secure access and confidentiality for participants. Each participant will be assigned a unique log-in name and password, which will provide them access to the eHealth Familias Unidas Primary Care session. The log-in procedure will also facilitate the close monitoring of participants, particularly as it relates to session participation rates. Specifically, the log-in procedure will be utilized to record who (i.e., which participant), when (i.e., day/time), how long (e.g., time of session attendance), and for what purpose (e.g., which session) the intervention website was accessed.

Our information technology team employs the latest technology to ensure security and confidentiality of participants, including but not limited to data error checking through forms, filtering output, and the use of encryption. Server Port Hardening will be implemented to keep

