the web server safe from intrusion. Additionally, a Secure Socket Layer Encryption certificate will be issued to help prevent Internet fraud. The implementation of SSLs (i.e., cryptographic protocols) aims to enhance security over the Internet. IT will conduct stringent testing of web applications prior to the implementation of eHealth Familias Unidas Primary Care to prevent any exploits from occurring and to ensure the confidentiality of participants.

ii) Control Condition

Participants randomized to the control condition continue prevention as usual. These participants will not be receiving any services from our staff. These participants will only be asked to complete a survey at each of the 5 time points: when they first enroll, and at 6, 12, 24, and 36 months. The adolescent will also be asked to provide a sample for an STI test during each of these time points.

(b) Assessments

After the intervention is complete, assessors will call the families to return to complete follow up assessments. The follow up assessments will occur on the University of Miami Miller School of Medicine Campus, at the clinic sites or at the homes of the participants. The follow up assessments collect the same data as the baseline assessment. All measures will be self-report and completed using survey software provided by the study team

(c) Data Collection

Demographics. A demographics form developed by the creators of Familias Unidas will be administered to caregivers and youth in order to collect information on contact information, age, date/place of birth, number of years residing in the U.S., parents' marital status, and family income.

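### The outcome assessors also track online-session progress, which reveals the arm to them, and the supplied text has no assessor masking or equal-contact safeguard

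*Combined protocol and SAP*

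**What the plan says.** The staff-roles text gives the assessor four duties.

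- Data collection: "Assessors are responsible for conducting the parent and youth assessments over the five years".
- Scheduling: "The assessor will also be responsible for scheduling these assessments".
- Retention: "the assessor will also be responsible for maintaining cordial contact in between assessment time points, in order to maximize retention rates at assessments".
- Intervention progress: "They will also be responsible for tracking family completion of online sessions and progression through the intervention". The sentence just before this one is about the assessor, so that is the natural reading of its subject.

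The control arm has nothing to track. Section 10(a)(ii) says of control families: "These participants will not be receiving any services from our staff", and "These participants will only be asked to complete a survey at each of the 5 time points", with an STI sample from the adolescent at each of those times.

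Section 10(a)(i) describes two other resources. Session use is captured by the website: "The log-in procedure will also facilitate the close monitoring of participants, particularly as it relates to session participation rates". The live sessions belong to a different role: "eHealth Familias Unidas Primary Care facilitators will be responsible for scheduling and delivering the four online family sessions with each of their families".

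The only blinding language in the supplied text is in section 7(a), where it describes how a family is randomized. It does not describe what assessors know afterwards.

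**The concern.** Families in this trial cannot be blinded, so the knowledge held by the person who runs the outcome visits matters more than usual. Two of the three primary outcomes, past 90-day drug use and unprotected sex, are sensitive adolescent self-reports. The family-functioning mediator is self-reported too. An assessor who has followed a family through a programme aimed at those behaviours may, without intending it, invite the answers that the programme promotes.

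The same person arranges follow-up visits and works to keep families in the study through 36 months. The power calculation in section 12(a) assumes the same loss in both arms, and nothing in the supplied text protects that assumption. Retention that differs by arm can bias all three primary comparisons, including the laboratory-based one, because PCR protects the result of a sample but not who provides it.

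**Working it through.** **Step 1. Does the duty reveal the arm?** Assessors track session completion (staff-roles text). Sessions exist in one arm only, and control families get no services from study staff (section 10(a)(ii)). An assessor carrying out the duty as written therefore knows which families are in the intervention arm and, by elimination, which are controls.

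**Step 2. Which routes to bias are open?**

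| Route | What the plan provides | Open? |
|---|---|---|
| Assessor scores the outcome | Self-report on survey software (10(b)), on a tablet (12(b)) | Largely closed |
| Assessor alters the STI result | PCR (10(c)) at an outside laboratory (12(c)) | Closed for the assay |
| Rapport, socially desirable answers | Adolescents answer apart from the caregiver (17); nothing on assessor masking | Open |
| Scheduling and retention effort | Assessor does both; no equal-effort rule | Open |
| Whether a follow-up sample is taken | Sample at each time point (10(a)(ii), 11), but section 26 ties follow-up screening to reported risk behaviour | Unclear; these passages must be reconciled |

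**Step 3. The plan's own retention figure.** Section 12(a) assumes 5% loss at each assessment: 228 × 0.95⁴ = 185.7 per arm, against the stated 185. It reproduces.

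**Step 4. Illustration of unequal retention for STI incidence (H1c).** The documents give no differential loss, so the inputs here are assumptions. Suppose the true 3-year risk is 9.2% in both arms (the plan's control figure, section 12(a)), a fraction r of an arm is retained, those lost have k times the risk of those retained, and those lost contribute no STI result. The observed incidence is then q = 0.092 / (r + (1 − r)k).

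Worked case: 3% loss per assessment in the intervention arm, 7% in control, k = 2.

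- Intervention: r = 0.97⁴ = 0.885, q = 0.092 / (0.885 + 0.115 × 2) = 8.25%.
- Control: r = 0.93⁴ = 0.748, q = 0.092 / (0.748 + 0.252 × 2) = 7.35%.
- Spurious difference: 8.25% − 7.35% = 0.9 points.

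| Loss per assessment, intervention vs control | Retained | Spurious difference, k = 1.5 to 3 |
|---|---|---|
| 5% vs 5% | 186 vs 186 | 0 |
| 4% vs 6% | 194 vs 178 | 0.3 to 0.7 points |
| 3% vs 7% | 202 vs 171 | 0.5 to 1.4 points |
| 2% vs 8% | 210 vs 163 | 0.8 to 2.1 points |

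The target difference in section 12(a) is 6.1 points. The total retained hardly changes (186 + 186 = 372; 194 + 178 = 372; 202 + 171 = 373; 210 + 163 = 373), so the issue is bias, not sample size.

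**Step 5. Direction.** In this illustration, better retention in the intervention arm works against the intervention. Socially desirable answering in that arm would work in its favour. The net sign cannot be predicted.

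**The case against.** The strongest reply is that the assessor scores no primary outcome. Adolescents enter their own answers on a tablet, away from the caregiver, and the STI result comes from an outside laboratory. That stands, and it keeps the concern modest. It does not reach rapport, scheduling or retention effort.

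A second reply is that a website log does not read itself, so somebody must review it. That also stands: tracking is a legitimate task. The question is only who does it, and the facilitators already know the arm because they deliver the family sessions.

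A third is that reassignment cannot deliver full masking. Randomization follows directly on the baseline assessment (sections 7(a) and 10(a)), so an assessor present then may learn the result, and families know their arm at every later visit. This is right, and the fix has to allow for it.

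A reader might go further and infer that intervention families get more assessor contact than controls. The documents do not support this. The retention contact is described without reference to arm, facilitators schedule the family sessions, and tracking from a log needs no contact. Nor do the documents support a reading that assessments are mostly held at home: sections 10(b) and 21 list campus, clinic and home without frequencies.

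**Conclusion.** The concern holds in a limited form. The tracking duty, followed as written, reveals the arm to the staff who run outcome visits and manage retention. The supplied text has no assessor masking and no rule for equal contact or retention effort. This is an avoidable weakness and cheap to remove, but it is not a demonstrated bias.

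Size and direction are unknown. The 0.3 to 2.1 points for STI incidence rest entirely on assumed loss rates and assumed risk among those lost, and show only the order of magnitude that uneven retention could produce. For the self-reported outcomes, a reader might want to turn a supposed reporting shift into an inflated type I error. The documents do not allow it: they give no size for such a shift, and the effect size of 0.3 in section 12(a) belongs to a difference in growth slopes, whereas a similar shift at every follow-up is a change in level that enters a slope only in part.

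One caveat on absence: some text next to the staff-roles passage is missing from the copy reviewed, so the lack of masking or contact rules applies to the supplied text only.

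**What to change.** In the staff-roles text:

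1. Take session tracking out of the assessors' duties and give it to the facilitators or the project coordinator, working from the website log-in records.
2. State that follow-up assessors are kept unaware of arm where feasible, and that they neither handle nor are told the randomization result after baseline.
3. Set one between-visit contact schedule that applies to both arms.
4. Report the number of contacts and the retention at each assessment by arm.

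Separately, reconcile section 26 with sections 10(a)(ii) and 11 on whether a follow-up urine sample depends on reported behaviour, so that no discretion over sampling rests with someone who knows the arm.

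The cost is protocol wording, a contact log, and some tracking time for facilitators or the coordinator. No new staff or visits are needed. Masking will remain imperfect because families know their arm and may disclose it.

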## 23) **Prior Approvals**

N/A

**24) Local Number of Subjects**

Approximately 2500 subjects will be screened, and 912 will be enrolled. Additionally approximately 12 parents and 12 adolescents will participate in the pilot study.

**25) Confidentiality**

The issues surrounding confidentiality are of supreme importance and sensitivity because personal information will be obtained from the adolescent and their family members. Participants sign a statement attesting to their understanding that the information they provide will be held as personal and confidential. Consent forms clearly state the right to refuse participation at any time. In addition, because this project involves the collection of drug use and sexual behavior information, to strengthen the security of our records in relation to local and state courts, a Confidentiality Certificate under section 502C of Part E, Title II of the Comprehensive Drug Abuse Prevention and Control Act of 1970, Public Law 91-513, has been obtained. This Certificate has been utilized in previous prevention studies and has been instrumental in maintaining the privacy/confidentiality of sensitive client information.

To assure confidentiality at STI testing during each time point, only the adolescent and the research assessor will be present (at the same time) during the procedure. Urine will be collected from the adolescent in a completely private manner; at no moment will the assessor watch the adolescent collect the urine specimen. Both the adolescent and the research assessor shall keep the adolescent's urine specimen in view at all times before the specimen is sealed and labeled. The research assessor will place an identification label securely on each container. The label will contain the adolescent's code number as the only source of identifying information. The assessor will drop off to study research offices the collected urine sample on the same day that it is collected.

In addition, we will do everything we can to keep others from learning about the participants in this study. As mentioned above, to help further protect their privacy, the study researchers have been granted a Federal Certificate of Confidentiality from the National Institutes of Health. With this Certificate, the researchers cannot be forced, even by a court order, to share research information that may identify the participants in any civil, criminal, administrative, legislative, or other proceedings in any court. The researchers will use the Certificate to resist any demands for information that would identify the participants, except to prevent serious harm to them or others, and as explained below.

The participants should understand that a Certificate of Confidentiality does not prevent them, or a member of their family, from voluntarily releasing information

about themselves, or their involvement in this study. If an insurer or employer learns about their participation, and obtains participant's consent to receive research information, then we may not use the Certificate of Confidentiality to withhold this information. This means that the participants and their family must also actively protect their own privacy. Disclosure will be necessary, however, upon request for the purpose of audit or evaluation, and is limited only to Department of Health and Human Services employees involved in the review. The participant should understand that we will in all cases, take the necessary action, which may include reporting to authorities, to prevent serious harm to themselves or others.

